17.2.1. LABORATORY REFERENCE RANGES AND AGE CRITERIA

Quantitative laboratory measurements will be compared with the relevant laboratory reference ranges in SI units and categorized as:

- Low: Below the lower limit of the laboratory reference range.
- Normal: Within the laboratory reference range (upper and lower limit included).
- High: Above the upper limit of the laboratory reference range.

In addition to the high and low quantitative laboratory assignments (as identified by means of the laboratory reference ranges), abnormalities will be classified as not clinically significant or clinically

Document: \\ieedc-vnasc01\BIOSdata\Abivax\ABX464\FZA92720\Biostatistics\Documentation\SAP\ABX464-103_SAP_V2.0_10MAY2021

Author: [REDACTED]

Version Number:

2.0

Version Date:

10May2021

Template No.: CS_TP_BS016 Revision 5

Reference: CS_WI_BS005

Effective Date: 01Apr2018

significant.

17.3. ECG EVALUATIONS

Overall assessment of the results from the central ECG Reading Center will be included in the reporting of this study and summarized by frequency and percentage of patients in each assessment category for every visit and treatment group.

Overall assessment of ECG (Investigator's judgment) will be reported as follows:

- Normal
- Abnormal NCS
- Abnormal CS

The following summaries will be provided for ECG data:

- Incidence of overall assessments (normal, abnormal NCS, abnormal CS)
- Shift from baseline according to overall assessment of ECG

17.4. VITAL SIGNS

Descriptive statistics including n, mean, SD, SEM, median, minimum and maximum will be summarized for all vital sign parameters.

The following vital sign measurements will be reported for this study:

- Systolic Blood Pressure (SBP) (mmHg)
- Diastolic Blood Pressure (DBP) (mmHg)
- Heart Rate (beats/min)
- Body Temperature (°C)
- Weight (kg)

Document: \\ieedc-vnasc01\BIOSdata\Abivax\ABX464\FZA92720\Biostatistics\Documentation\SAP\ABX464-103_SAP_V2.0_10MAY2021

Author: [REDACTED]

Version Number: 2.0
Version Date: 10May2021

Template No.: CS_TP_BS016 Revision 5

Reference: CS_WI_BS005

Effective Date: 01Apr2018

- Baseline Height (cm)
- BMI (kg/m²)

The following summaries will be provided for vital signs data:

- Actual and change from baseline by visit
- Incidence of clinically significant abnormal results for each parameter and visit
- Shift table for number of patients with abnormal results
- Listing of results by patient, including abnormal observations

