9.3. Safety Analyses

Adverse events will be coded using the standard dictionary (MedDRA) down to the lower level term (LLT).

An overall summary table will be presented (Any adverse event, any treatment emergent adverse event (TEAE), any serious adverse event (SAE), death, any grade 3 or higher adverse events from baseline to the end of Study. This analysis will be conducted on SAF population.

Two periods will be defined for TEAE:

- Any adverse event which occurs or worsens from first dosing to Day 113;
- Any adverse event which occurs after Day 113.

Adverse events will be described by primary system organ class and preferred term. Numbers and percentage of patients, and number of occurrences of adverse event will be presented for:

- TEAE;
- Serious TEAE;
- TEAE leading to drug discontinuation;
- TEAE of grade 3 or 4;
- TEAE for which relationship with the study drug is recorded as possible or probable;
- TEAE leading to death.

The assessment of safety will be based on the frequency of adverse events (with and without regard to causality) graded according to the CTC-AE Classification and also, the review of individual values for clinical laboratory data, vital signs and ECG focusing on the detection of abnormal values and PCSAs as determined upon investigator considerations.

Adverse events will be tabulated (counts and percentages) by group. All adverse events will be listed and the data will be tabulated by body system/organ class. Adverse event tabulations will include all treatment emergent adverse events, which will be further classified by severity, and relationship to treatment and dose level.

Clinical laboratory parameters, vital signs, ECG will be summarized by using descriptive statistics (n, mean, SD, SEM, median, minimum and maximum). Number of patients with at least one abnormal values will be tabulated (counts and percentages) for each parameter in summary shift tables, by group and dose.

9.3.1.Clinical laboratory evaluation

Descriptive statistics for laboratory parameters will be computed at each scheduled assessment. If relevant for some parameter, change from baseline will also be tabulated.

In addition, shift tables from baseline will be presented.

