17.4.1. VITAL SIGNS CLINICALLY SIGNIFICANT CRITERIA

Abnormal vital sign assessments will be reported in accordance with the following predefined abnormal criteria:

Variable	Unit	Low	High
SBP	mmHg	≤ 90 mmHg AND change from baseline ≤ -20 mmHg	≥ 180 mmHg AND change from baseline ≥ 20 mmHg
DBP	mmHg	≤ 50 mmHg AND change from baseline ≤ -15 mmHg	≥ 105 mmHg AND change from baseline ≥ 15 mmHg
Heart rate	Bpm	≤ 50 bpm AND change from baseline ≤ -15 bpm	≥ 120 bpm AND change from baseline ≥ 15 bpm
Body temperature	°C	NA	≥ 38.3 °C AND change from baseline ≥ 1.1 °C
Weight	Kg	percentage change from baseline ≤ -7.0 %	percentage change from baseline ≥ 7.0 %

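### SAP 17.4.1 makes every vital-sign abnormality depend on a change from baseline, so the 17.4 shift table has only one baseline category and leaves small-change crossings of a level limit uncounted

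*SAP*

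**What the plan says.** SAP 17.4 lists several vital-sign outputs. Two are categorical: the incidence of clinically significant abnormal results by parameter and visit, and a "Shift table for number of patients with abnormal results".

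SAP 17.4.1 then supplies the definition: "Abnormal vital sign assessments will be reported in accordance with the following predefined abnormal criteria". The table below that sentence joins a level and a change for four parameters:

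- Systolic pressure: low if "≤ 90 mmHg AND change from baseline ≤ -20 mmHg"; high if "≥ 180 mmHg AND change from baseline ≥ 20 mmHg".
- Diastolic pressure: low if "≤ 50 mmHg AND change from baseline ≤ -15 mmHg"; high if "≥ 105 mmHg AND change from baseline ≥ 15 mmHg".
- Heart rate: low if "≤ 50 bpm AND change from baseline ≤ -15 bpm"; high at 120 bpm or more with a rise of at least 15.
- Temperature: high only, at 38.3 °C or more with a rise of at least 1.1 °C.

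Weight has no level limit and is judged by a change of 7% in either direction. Height and BMI, also listed in 17.4, have no criterion.

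SAP 6.6 defines change as the visit value minus the baseline value, and SAP 6.2 fixes one baseline value per patient. Protocol 9.3 sets the requirement for laboratory, vital-sign and ECG data: "Number of patients with at least one abnormal values will be tabulated (counts and percentages) for each parameter in summary shift tables".

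**The concern.** A shift table cross-classifies patients by category at baseline and category on treatment. The rule therefore has to be one that a baseline value can satisfy. The SAP's other shift tables meet that condition. Laboratory values (SAP 17.2) are low, normal or high against reference ranges, and ECGs (SAP 17.3) are normal, abnormal not clinically significant or abnormal clinically significant. The vital-sign rule does not meet it, because it is itself a statement about change.

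Two things are at stake in the safety report. A patient who enters the trial already beyond a level limit is shown as not abnormal at baseline. A patient who crosses a level limit on treatment by a modest change is shown as not abnormal both before and after.

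**Working it through.** The documents state no figure on this point, so there is none to reproduce. The check applies the 17.4.1 criteria as written.

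**Step 1: the baseline category.** Let B be the baseline value and V the value being classified. For the baseline value itself V = B, so the change is B − B = 0, and the percentage change for weight is 0 × 100 / B = 0%. The conditions require a change of ≤ −20 or ≥ 20 (systolic), ≤ −15 or ≥ 15 (diastolic and heart rate), ≥ 1.1 °C (temperature), or ≤ −7% or ≥ 7% (weight). Zero meets none of them. All five parameters have one baseline category, not abnormal, whatever the value; a baseline systolic pressure of 185 falls in it.

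**Step 2: new crossings that are not counted.** Take a lower limit L with required fall d. A patient in range at baseline (B > L) crosses the limit without being flagged when V ≤ L but V > B − d. In whole units such a V exists only if B < L + d, so the baselines concerned run from L + 1 to L + d − 1. For an upper limit U the same argument gives U − d + 1 to U − 1. Temperature is taken in steps of 0.1 °C.

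| Parameter | Limit | Required change | Baselines from which a crossing can go uncounted |
|---|---|---|---|
| Systolic, low | 90 | 20 | 90 + 1 = 91 to 90 + 19 = 109 |
| Systolic, high | 180 | 20 | 180 − 19 = 161 to 179 |
| Diastolic, low | 50 | 15 | 51 to 50 + 14 = 64 |
| Diastolic, high | 105 | 15 | 105 − 14 = 91 to 104 |
| Heart rate, low | 50 | 15 | 51 to 50 + 14 = 64 |
| Heart rate, high | 120 | 15 | 120 − 14 = 106 to 119 |
| Temperature, high | 38.3 | 1.1 | 38.3 − 1.0 = 37.3 to 38.2 |

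These are baselines from which a crossing can be missed, not baselines from which it always is. For a lower limit, the number of whole values that escape is L + d − B. From a systolic baseline of 109 it is 90 + 20 − 109 = 1 (the value 90 only); from 91 it is 90 + 20 − 91 = 19 (values 72 to 90).

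**Step 3: individual records scored literally.**

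| Baseline → on treatment | Change | Under 17.4.1 | By level limit alone |
|---|---|---|---|
| Systolic 185 → 190 | +5 | not abnormal → not abnormal | high → high |
| Systolic 165 → 182 | +17 | not abnormal → not abnormal | normal → high |
| Systolic 105 → 88 | −17 | not abnormal → not abnormal | normal → low |
| Diastolic 60 → 48 | −12 | not abnormal → not abnormal | normal → low |
| Heart rate 60 → 48 | −12 | not abnormal → not abnormal | normal → low |
| Temperature 37.4 → 38.4 | +1.0 | not abnormal → not abnormal | normal → high |
| Systolic 150 → 185 | +35 | not abnormal → high | normal → high |
| Heart rate 80 → 125 | +45 | not abnormal → high | normal → high |

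The last two rows show that a crossing with a large enough change is flagged under either rule.

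**The case against.** **The shift table may use another definition.** Section 17.4.1 is headed as criteria for clinical significance, and 17.4 names clinically significant abnormal results for the incidence table but plain abnormal results for the shift table. Protocol 5.3.1 speaks of normal ranges and alert limits for vital signs, and SAP section 8 leaves table content to templates that are not among the documents. So the authors may have had a second notion of abnormal in mind. What stands is that the wording is not fully settled. But no other range is given in either document, and the opening sentence of 17.4.1 applies its criteria to abnormal assessments in general. SAP 3.3 drops potentially clinically significant abnormalities for lack of data and puts no vital-sign range in their place. A programmer working from the SAP has only the joint criteria.

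**Requiring both a level and a change is a legitimate choice.** This stands for the incidence of clinically significant results, where the joint rule keeps small fluctuations near a limit from being counted. It does not help a table that needs a baseline category.

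**The information survives elsewhere.** This also stands. SAP 17.4 plans actual values and changes by visit, with minimum and maximum, and a patient listing. Protocol 5.3.1 has investigators assess out-of-range values and record clinically significant ones as adverse events.

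**A stronger reading is tempting: that the shift table adds nothing to the incidence table.** The documents do not support it. The incidence table is by visit. Under SAP 6.3, unscheduled measurements stay out of by-visit summaries but feed the worst value used in a shift table, and Protocol 9.3 asks for patients with at least one abnormal value. The shift table can therefore still give a per-patient worst-case count that the incidence table does not.

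**Conclusion.** The point holds as a minor defect in descriptive safety reporting. On the text of 17.4.1 and 6.6, 100% of patients fall in one baseline category. The shift table cannot show who was already beyond a level limit at baseline, and it leaves uncounted those new crossings whose change falls short of the threshold, from the baselines tabulated above.

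The conclusion assumes that 17.4.1 governs the shift table and that the templates set no other categories. How many patients would be affected cannot be computed, because the documents give no vital-sign distributions.

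A reader might infer that new out-of-range values are hidden in general, or that a safety signal would be lost. Neither follows: crossings with a change at or above the threshold are flagged, and the values appear in the by-visit statistics and the listing. SAP section 17 plans no between-group comparison of safety data unless specified, and the efficacy analyses are untouched.

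**What to change.** Amend SAP 17.4 to say:

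- The shift table covers systolic pressure, diastolic pressure, heart rate and temperature. It classifies both the baseline value and the worst on-treatment value, unscheduled values included as SAP 6.3 allows, by the level limits already in 17.4.1 and nothing else: ≤ 90 / ≥ 180 mmHg, ≤ 50 / ≥ 105 mmHg, ≤ 50 / ≥ 120 bpm, and ≥ 38.3 °C (high only). It should also say how a patient with both a low and a high on-treatment value is shown.
- The joint level-and-change criteria are kept for the incidence of clinically significant results.
- Weight, which has no level limit, is left out of the shift table and reported by the percentage-change incidence only.

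The cost is two or three SAP sentences, a matching line in the table template and a small programming change. No new data are needed.

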17.4.1. VITAL SIGNS CLINICALLY SIGNIFICANT CRITERIA

Abnormal vital sign assessments will be reported in accordance with the following predefined abnormal criteria:

Variable	Unit	Low	High
SBP	mmHg	≤ 90 mmHg AND change from baseline ≤ -20 mmHg	≥ 180 mmHg AND change from baseline ≥ 20 mmHg
DBP	mmHg	≤ 50 mmHg AND change from baseline ≤ -15 mmHg	≥ 105 mmHg AND change from baseline ≥ 15 mmHg
Heart rate	Bpm	≤ 50 bpm AND change from baseline ≤ -15 bpm	≥ 120 bpm AND change from baseline ≥ 15 bpm
Body temperature	°C	NA	≥ 38.3 °C AND change from baseline ≥ 1.1 °C
Weight	Kg	percentage change from baseline ≤ -7.0 %	percentage change from baseline ≥ 7.0 %

17.5. PHYSICAL EXAMINATION

The following assessments will be taken at every physical examination: eyes, ears, nose and throat, lungs/thorax, heart/cardiovascular system, abdomen, skin and mucosae, nervous system, lymph nodes and

Document: \\ieedc-vnasc01\BIOSdata\Abivax\ABX464\FZA92720\Biostatistics\Documentation\SAP\ABX464-103_SAP_V2.0_10MAY2021

Author: [REDACTED]

Version Number: 2.0
Version Date: 10May2021

Template No.: CS_TP_BS016 Revision 5

Reference: CS_WI_BS005

Effective Date: 01Apr2018

musculo-skeletal system.

Results will be captured by the following categories:

- Normal
- Abnormal, NCS
- Abnormal, CS

Only abnormal findings will be presented in a listing.

Document: \\ieedc-vnasc01\BIOSdata\Abivax\ABX464\FZA92720\Biostatistics\Documentation\SAP\ABX464-103_SAP_V2.0_10MAY2021

Author: [REDACTED]

Version Number: 2.0
Version Date: 10May2021

Template No.: CS_TP_BS016 Revision 5

Reference: CS_WI_BS005

Effective Date: 01Apr2018

APPENDIX 1. PROGRAMMING CONVENTIONS FOR OUTPUTS

IQVIA OUTPUT CONVENTIONS

Outputs will be presented according to the guidelines in the IQVIA Biostatistics Output Conventions.

DATES & TIMES

Depending on data available, dates and times will take the form yyyy-mm-ddThh:mm:ss.

SPELLING FORMAT

English US

PRESENTATION OF TREATMENT GROUPS

For outputs, treatment groups will be represented as follows and in that order:

Treatment Group	For Tables, Listings and Graphs
ABX464 100 mg	100 mg
ABX464 50 mg	50 mg
ABX464 25 mg	25 mg
Placebo	Placebo
Not Treated	Not Treated
Not Randomized	Not Randomized

PRESENTATION OF VISITS

For outputs, visits will be represented as follows and in that order:

Document: \\ieedc-vnasc01\BIOSdata\Abivax\ABX464\FZA92720\Biostatistics\Documentation\SAP\ABX464-103_SAP_V2.0_10MAY2021

Author: [REDACTED]

Version Number: 2.0
Version Date: 10May2021

Template No.: CS_TP_BS016 Revision 5

Reference: CS_WI_BS005

Effective Date: 01Apr2018

Long Name (default)	Short Name
Screening	SC
Randomization	Randomization
Baseline (Day 1)	Baseline
Day 8	D8
Day 29	D29
Week 8 (Day 57)	D57
Day 85	D85
Week 16 (Day 113)	D113
EOS (Day 120)	EOS

LISTINGS

All listings will be ordered by the following (unless otherwise indicated in the template):

- Treatment
- Site-Patient ID
- Date (where applicable)
- For listings where not treated or non-randomized patients are included, these will appear in a category after the randomized treatment groups labelled “Not Treated” and “Not Randomized”.

Document: \\ieedc-vnasc01\BIOSdata\Abivax\ABX464\FZA92720\Biostatistics\Documentation\SAP\ABX464-103_SAP_V2.0_10MAY2021

Author: [REDACTED] Version Number: 2.0
Version Date: 10May2021

Template No.: CS_TP_BS016 Revision 5

Reference: CS_WI_BS005

Effective Date: 01Apr2018

APPENDIX 2. MAYO SCORE

Components of the Mayo Score	
Stool frequency	
0	Normal
1	1–2 stools/day more than normal
2	3–4 stools/day more than normal
3	5 or more stools/day more than normal
Rectal bleeding	
0	None
1	Visible blood with stool less than half the time
2	Visible blood with stool half of the time or more
3	Passing blood alone
Mucosal appearance at endoscopy	
0	Normal or inactive disease
1	Mild disease (erythema, decreased vascular pattern, mild friability)
2	Moderate disease (marked erythema, absent vascular pattern, friability, erosions)
3	Severe disease (spontaneous bleeding, ulceration)
Physician rating of disease activity	
0	Normal
1	Mild
2	Moderate
3	Severe

Document: \\ieedc-vnasc01\BIOSdata\Abivax\ABX464\FZA92720\Biostatistics\Documentation\SAP\ABX464-103_SAP_V2.0_10MAY2021

Author: [REDACTED] Version Number: 2.0
Version Date: 10May2021

Template No.: CS_TP_BS016 Revision 5

Reference: CS_WI_BS005

Effective Date: 01Apr2018

APPENDIX 3. PARTIAL DATE CONVENTIONS

Imputed dates will NOT be presented in the listings.

ALGORITHM FOR TREATMENT EMERGENCE OF ADVERSE EVENTS:

START DATE	STOP DATE	ACTION
Known	Known/Partial/Missing	If start date < study med start date, then not TEAE If start date >= study med start date, then TEAE
Partial, but known components show that it cannot be on or after study med start date	Known/Partial/Missing	Not TEAE
Partial, could be on or after study med start date	Known	If stop date < study med start date, then not TEAE If stop date >= study med start date, then TEAE
	Partial	Impute stop date as latest possible date (i.e. last day of month if day unknown or 31st December if day and month are unknown), then: If stop date < study med start date, then not TEAE If stop date >= study med start date, then

Document: \\ieedc-vnasc01\BIOSdata\Abivax\ABX464\FZA92720\Biostatistics\Documentation\SAP\ABX464-103_SAP_V2.0_10MAY2021

Author: [REDACTED]

Version Number: 2.0
Version Date: 10May2021

Template No.: CS_TP_BS016 Revision 5

Reference: CS_WI_BS005

Effective Date: 01Apr2018

START DATE	STOP DATE	ACTION
		TEAE
	Missing	Assumed TEAE
Missing	Known	If stop date < study med start date, then not TEAE If stop date >= study med start date, then TEAE
	Partial	Impute stop date as latest possible date (i.e. last day of month if day unknown or 31st December if day and month are unknown), then: If stop date < study med start date, then not TEAE If stop date >= study med start date, then TEAE
	Missing	Assumed TEAE

ALGORITHM FOR PRIOR / CONCOMITANT MEDICATIONS:

START DATE	STOP DATE	ACTION
Known	Known	If stop date < study med start date, assign as prior If stop date >= study med start date and start date <= end of treatment, assign as concomitant

Document: \\ieedc-vnasc01\BIOSdata\Abivax\ABX464\FZA92720\Biostatistics\Documentation\SAP\ABX464-103_SAP_V2.0_10MAY2021

Author: [REDACTED]

Version Number: 2.0
Version Date: 10May2021

Template No.: CS_TP_BS016 Revision 5

Reference: CS_WI_BS005

Effective Date: 01Apr2018

START DATE	STOP DATE	ACTION
	Partial	Impute stop date as latest possible date (i.e. last day of month if day unknown or 31st December if day and month are unknown), then: If stop date < study med start date, assign as prior If stop date >= study med start date and start date <= end of treatment, assign as concomitant
	Missing	If stop date is missing could never be assumed a prior medication If start date <= end of treatment, assign as concomitant
Partial	Known	Impute start date as earliest possible date (i.e. first day of month if day unknown or 1st January if day and month are unknown), then: If stop date < study med start date, assign as prior If stop date >= study med start date and start date <= end of treatment, assign as concomitant
	Partial	Impute start date as earliest possible date (i.e. first day of month if day unknown or 1st January if day and month are unknown) and impute stop date as latest possible date (i.e. last day of month if day unknown or 31st December if day and month are unknown), then: If stop date < study med start date, assign as prior If stop date >= study med start date and start date <= end of treatment, assign as concomitant
	Missing	Impute start date as earliest possible date (i.e. first day of month if day unknown or 1st January if day and month are unknown), then: If stop date is missing could never be assumed a prior medication If start date <= end of treatment, assign as concomitant

Document: \\ieedc-vnasc01\BIOSdata\Abivax\ABX464\FZA92720\Biostatistics\Documentation\SAP\ABX464-103_SAP_V2.0_10MAY2021

Author: [REDACTED]

Version Number: 2.0
 Version Date: 10May2021

Template No.: CS_TP_BS016 Revision 5

Reference: CS_WI_BS005

Effective Date: 01Apr2018

START DATE	STOP DATE	ACTION
Missing	Known	If stop date < study med start date, assign as prior If stop date >= study med start date, assign as concomitant
	Partial	Impute stop date as latest possible date (i.e. last day of month if day unknown or 31st December if day and month are unknown), then: If stop date < study med start date, assign as prior If stop date >= study med start date, assign as concomitant
	Missing	Assign as concomitant

Document: \\ieedc-vnasc01\BIOSdata\Abivax\ABX464\FZA92720\Biostatistics\Documentation\SAP\ABX464-103_SAP_V2.0_10MAY2021

Author: [REDACTED]

Version Number: 2.0
Version Date: 10May2021

Template No.: CS_TP_BS016 Revision 5

Reference: CS_WI_BS005

Effective Date: 01Apr2018

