1.2.5.2. Previous clinical experience with ABX464

The effect of ABX464 in humans has been assessed in 5 completed clinical studies in healthy volunteers and in patients with HIV as well as in 1 completed study in patients with UC (ABX464-101). In addition, there is efficacy and safety data available from an interim analysis of the longer-term maintenance Study ABX464-102 in UC. Two further studies in UC (ABX464-103; ABX464-104) and 2 studies in RA (ABX464-301; ABX464-302) are ongoing. As of October 31, 2019, 211 subjects have received single doses (25 to 200 mg) of ABX464, or repeated doses (50 to 150 mg) up to a maximum duration approaching 2 years. An additional 18 subjects have received ABX464 or placebo in ongoing blinded studies.

ABX464 was rapidly absorbed and metabolised into ABX464-N-Glu within about 1 hour of treatment whatever the dose. After repeated administrations of ABX464, an initial decrease in ABX464 AUC was observed until steady state was reached after 4 weeks of treatment. Exposure to ABX464-N-Glu was much higher than to ABX464 in all patients. Food significantly increased ABX464 exposure, at least 2.8-fold.3.

Overall, the safety profile of ABX464 is acceptable; 8 serious AEs have been reported with ABX464, which were all considered not related to the investigational product. The most frequently reported AEs were nausea, vomiting and headache which were of mild to moderate intensity, occurring after treatment onset and transient in nature. The anticipated ABX464 adverse events are: Nausea, Vomiting, Abdominal pain upper, Abdominal pain, Diarrhea and Headache

For further information, please refer to the current Investigator's Brochure.

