8. ADVERSE EVENTS (AE) AND SERIOUS ADVERSE EVENTS (SAE)

The investigator is responsible for the detection and documentation of events meeting the criteria and definition of an AE or SAE. During the study, in case of a safety evaluation, the investigator or site staff will be responsible for reporting AEs and SAEs, as detailed in this section of the protocol.

During the screening period, all adverse events will be collected.

Any disease progression will be reported in the eCRF both as an adverse event and documented in the efficacy section.

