8.6. Recording AEs and SAEs

Severity of AEs will be assessed according to CTC-AE Classification Version 5.0.

Patients will be asked to report all AEs as part of the procedures performed at each study visit. The site personnel will document all AEs in the patient's medical record. All AEs subsequently must be recorded in the appropriate eCRF sections.

The following points must be recorded for each event:

- A description of the event in medical terms, not as reported by the patient;
- Date of onset (start date);
- Date of resolution (stop date);
- The time of onset with respect to administering the investigational medicinal product;
- The severity of the sign/symptom or clinically significant abnormal laboratory value according to CTC-AE Classification (Version 5.0);
- The causal relationship between the investigational medicinal product and the occurrence of each AE. This will be assessed by each investigator using clinical judgment. Alternative causes, such as natural history of the underlying diseases, concomitant medications, other risk factors and the temporal relationship of the event to the investigational medicinal product will have to be considered. The causality of all AEs should be assessed by the investigator with the following question: Is there a reasonable possibility that the AE may have been caused by the investigational medicinal product? And answered "NO" (if not related) and "YES" (if related);
- Action taken regarding the investigational medicinal product:
 - No action;
 - Temporary discontinuation;
 - Permanent discontinuation;

- Recovered without sequelae / resolved without sequelae;
- Recovered with sequelae / resolved with sequelae;
- Recovering/Resolving;
- On-going;
- Fatal (for SAEs only).

- Patient's outcome.

If in any one patient, the same AE occurs on several occasions, the AE in question must be documented and assessed a new each time.

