17.1. ADVERSE EVENTS

Adverse Events will be coded using the latest version of MedDRA, down to the lower level term (LLT).

Treatment emergent adverse events (TEAEs) are defined as AEs that started or worsened in severity on or after the first dose of study medication. As AEs will be recorded up to 4 weeks after study drug treatment has ended, AE will be considered treatment-emergent even if started after the last dose date. Adverse

Document: \\iedc-vnasc01\BIOSdata\Abivax\ABX464\FZA92720\Biostatistics\Documentation\SAP\ABX464-103_SAP_V2.0_10MAY2021

Author: [REDACTED]

Version Number: 2.0
Version Date: 10May2021

Template No.: CS_TP_BS016 Revision 5

Reference: CS_WI_BS005

Effective Date: 01Apr2018

events occurring after Day 113 will be flagged in the AE listing.

An overall summary of number of patients within each of the categories described in the sub-sections below, as well as the number of occurrences of the AE will be provided as specified in the templates. Listings will include TEAEs and Non-TEAEs.

See APPENDIX 3 for handling of partial dates for AEs. In the case where it is not possible to define an AE as treatment emergent or not, the AE will be classified by the worst case; i.e. treatment emergent.

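### The SAP Appendix 3 algorithm tests dates only, so an AE that begins between consent and first dose and worsens on treatment under its original record is classed as not treatment-emergent, against SAP 17.1 and Protocol 9.3

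*SAP*

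**What the plan says.** SAP 17.1 defines TEAEs as "AEs that started or worsened in severity on or after the first dose of study medication". Protocol 9.3 describes its on-treatment TEAE period in the same way: "Any adverse event which occurs or worsens from first dosing to Day 113". Both definitions have two arms, onset and worsening.

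SAP Appendix 3 contains the algorithm for treatment emergence. Two of its rows deal with AEs known to have begun before dosing:

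- Known start date, whatever the stop date: "If start date < study med start date, then not TEAE".
- A partial start date, described as "Partial, but known components show that it cannot be on or after study med start date": also not a TEAE, again whatever the stop date.

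No row of the algorithm mentions severity or worsening. SAP 17.1 refers to Appendix 3 for partial dates and adds a worst-case rule, under which an AE counts as treatment-emergent when its status cannot be decided. SAP 3.3, which lists changes from the protocol analysis, does not mention the TEAE definition.

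**The concern.** The definition and the rule that a programmer would code give opposite answers for the same event. Such events can exist in the database. Protocol 8 says "During the screening period, all adverse events will be collected", and Protocol 3.2 allows a screening period of up to 31 days.

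The anticipated drug effects are common symptoms that can also arise during screening. Protocol 1.2.5.2 states: "The anticipated ABX464 adverse events are: Nausea, Vomiting, Abdominal pain upper, Abdominal pain, Diarrhea and Headache". If one of these begins in screening and becomes more severe on drug, the worsening is what a TEAE table is meant to show.

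The study is a dose-selection trial, and the safety of each dose against placebo is a stated secondary objective. If worsening on treatment depended on dose, leaving these events out would move the TEAE comparison towards no difference. Two programmers working from the same SAP, one from 17.1 and one from Appendix 3, could also produce different TEAE tables.

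**Working it through.** The plan states no figure to reproduce. The check follows one hypothetical event through each rule: a headache of grade 1 starting on Day -5, still present on Day 1, reaching grade 3 on Day 10, and held as one AE record with its original start date.

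1. **SAP 17.1.** Severity rose after first dose, so the event is a TEAE.
2. **Protocol 9.3.** It worsened between first dosing and Day 113, so it is a TEAE.
3. **Appendix 3, known start date.** Day -5 precedes the study medication start date, so it is not a TEAE. The stop date and the grade play no part.
4. **Appendix 3, partial start date that must be pre-dose.** The same event with only a month recorded, that month lying wholly before dosing, is also not a TEAE.
5. **Worst-case rule in SAP 17.1.** This is not reached, because steps 3 and 4 give a definite class.

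The remaining rows show that the problem is the missing severity test. An AE with a missing start date and a stop date on or after first dose is a TEAE even if it never worsened. An AE with a known pre-dose start that did worsen is not.

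**Does the recording rule remove the problem?** Protocol 8.6 requires fresh documentation when "the same AE occurs on several occasions, the AE in question must be documented" and assessed again each time. That covers recurrence, not a rise in grade of a continuing event. The items listed in 8.6 include a start date, a stop date and the severity, but no date of worsening. If the eCRF nevertheless opens a new record at each increase in grade, that record has a post-dose start and Appendix 3 classes it correctly. The eCRF (Version 10 in the SAP references) is not among the documents, so this cannot be settled here.

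**Which outputs are affected.** Programmed as written, the event leaves the summaries restricted to TEAEs:

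- all TEAEs by maximum severity and by relationship (SAP 17.1.1);
- serious TEAEs (17.1.2);
- TEAEs leading to discontinuation of medication or of the study (17.1.3, 17.1.4);
- TEAEs leading to death (17.1.5);
- treatment-emergent AEs of special interest (17.1.6).

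It stays in the listings, which cover TEAEs and non-TEAEs (17.1) and all SAEs (17.1.2). It also stays in the overall table of Protocol 9.3, whose any-AE, any-SAE and grade 3 or higher counts are not limited to TEAEs. That table runs from baseline to end of study; I read this as including an event that is ongoing and worsens in that period.

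**Size per patient.** With 61 patients planned per arm (Protocol 9.4), k affected patients lower that arm's TEAE incidence for the term by k/61:

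- k = 1: 1/61 = 1.6 percentage points
- k = 2: 2/61 = 3.3 percentage points
- k = 3: 3/61 = 4.9 percentage points

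The documents give no information on k. The safety set counts treated patients, so the denominator may be slightly below 61.

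**The case against.** The best defence is that Appendix 3 is headed as a partial-date convention and 17.1 sends the reader there only for partial dates, so the main-text definition governs. As an account of the intention that is probably right, and SAP 3.3 records no departure from the definition. It does not remove the conflict, because the first row of the algorithm deals with fully known start dates.

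A second defence is that other protocol text captures worsening. Protocol 8.1.1 includes exacerbated symptoms and diseases among AEs, and 8.4.1 makes laboratory and other abnormalities present at consent reportable if they worsen significantly. This stands in part. A worsening entered as its own AE has a post-dose start and is classed correctly. Neither section says what onset date to enter, or requires a new record for an AE that is already open.

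A reader might infer that the symptoms of active colitis which patients bring into the trial, such as abdominal pain or diarrhoea, would be lost from the TEAE tables whenever the drug makes them worse, and that a sizeable dose difference would be hidden. The documents do not support this. Conditions already present at consent would mostly be held as medical history, which has an ongoing flag (SAP 5.2.4, criterion 11). They would enter as AEs only on exacerbation, which can give a post-dose start. The documents also offer no frequency from which a hidden difference between arms could be calculated. Nor do the events vanish from all safety reporting, as the list of outputs above shows.

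**Conclusion.** The point holds for a narrow group: AEs that start between consent and first dose, are ongoing at first dose, rise in grade on treatment and keep their original record. For these, Appendix 3 gives the wrong class under the plan's own definition in SAP 17.1 and Protocol 9.3.

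The effect on results rests on two conditions that the documents cannot confirm: that the tables are programmed from Appendix 3 as written, and that the eCRF does not open a new record when an ongoing AE increases in grade. The number of such events is unknown. The only size that can be stated is about 1.6 percentage points of TEAE incidence per affected patient in an arm of 61. The direction is towards too few TEAEs. Whether that differs by dose cannot be judged from the documents. The contradiction in the text remains whatever the eCRF does and should be corrected.

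**What to change.** 1. In both pre-dose rows of Appendix 3 (known start date, and partial date that must be pre-dose), replace the outcome with: *not TEAE unless severity increased on or after study medication start date, then TEAE*.
2. State in Appendix 3 that the definition in SAP 17.1 governs if the two differ.
3. Before database lock, confirm how the eCRF records an increase in grade of an ongoing AE. If a new record is opened, say so in the SAP and apply the algorithm to that record. If not, query the AEs ongoing at first dose for the grade before and after dosing, so that the new branch can be applied.

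Protocol 9 allows documented SAP amendments before final database lock. The SAP is dated 10 May 2021 and the planned study period ends in Q2 2021, so new guidance to sites would come late, and step 3 relies on queries instead. Where only one severity was entered, those queries need checking against source records. The cost is two changed rows, one added sentence, a small number of queries and slightly higher TEAE counts.
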